#### 4.2. Inclusion Criteria

Patients must satisfy all of the following criteria during screening to be enrolled in the study:

1. Has given voluntary written informed consent before performance of any study related procedure.
2. Must be 18 to 65 years of age, inclusive
3. Are on stable NA therapy at least 12 months from the screening date (ETV or TDF)
4. Has virally suppressed CHB:
  - a. HBV DNA <LLOQ and serum HBsAg >100 IU/mL
5. Has liver imaging to screen for hepatocellular carcinoma or concomitant pancreaticobiliary disease either in the prior 6 months or at screening.
6. Has liver tests during the Screening Period defined as follows:
  - a. The baseline values (i.e. two measurements at least 3 days apart: one can be

---

 The performance characteristics of the quantitative HBV DNA assay will be reported in the laboratory manual. The same assay will be used for all study visits. An FDA approved test will be used such as Abbott Realtime HBV Assay or COBAS HBV Test.

 Or equivalent effective NA: Lamivudine, adefovir dipivoxil, ETV, telbivudine and TDF have been approved in most Asia Pacific countries. Patients will be switched to ETV 0.5 mg or Tenofovir Disoproxil 245 mg or Tenofovir Disoproxil Fumarate (TDF) 300 mg during screening period if they are not already taking this drug with the same dosage or equivalent.

 Genotype information will be collected from medical history, if not available best effort to assess in virologically appropriate plasma sample will be used.

 The performance characteristics of the HBsAg quantitative assay will be reported in the laboratory manual. The same assay will be used for all study visits. A validated test will be used (such as Quest Diagnostics quantitative HBsAg or DIASORIN LIAISON® XL HBsAg Quant ([REF] 310250).

Rational: HBsAg level <100 IU/mL predictive for sustained response 2 years after EOT. The role of HBsAg levels in the current management of chronic HBV infection [Höner et al, 2014].

 Cross resistance has been described between lamivudine and ETV, as well as telbivudine. In case of previous therapy with lamivudine or telbivudine and current treatment with ETV, a possible cross resistance must be documented as to be unlikely by appropriate in vitro testing (mutational analysis M204V/I, rtT184, rtS202, or rtM250), else history of previous Lamivudine therapy leads to exclusion.

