## **11. Statistical Methods and Determination of Sample Size**

### **11.1. Statistical Analysis Plan and General Statistical Methods**

All data will be handled and processed according to the sponsor's representative (Novotech [Australia] Pty Ltd) SOPs, which are written based on the principles of GCP.

A Statistical Analysis Plan (SAP) containing the detailed planned statistical methods will be finalized prior to locking of the study database for the interim and final analysis and will form the basis for the programming of the displays and analyses of the final study data. All statistical calculations will be performed using SAS® (SAS Institute Inc., Cary, NC, USA) or similar software.

The statistical analyses will consist of both inferential and descriptive statistics. In general, the data will be presented by dose group. All collected and derived data will be included in the patient data listings.

All inferential analyses will be conducted at a one-sided 0.05 level of significance. Unless otherwise specified, all inferential testing will be one-sided in nature.

Continuous data, other than PK data, will be summarized by treatment group and time point using the number of observations, arithmetic mean, standard deviation, median, minimum and maximum. The coefficient of variance, geometric means and geometric coefficient of variance will also be presented for the concentration-related PK data. Categorical data will be summarized by the number and percentage of patients in each category. Unless specifically stated otherwise, the number of patients in the treatment group (for the specific analysis set) will be used as the denominator for all percentage calculations.

Baseline is defined as the last available non-missing value collected prior to the first administration of IP.

Change from baseline values will be calculated as the difference between the result at a specific time point, and the baseline value for the specific endpoint.

Missing, unused, or spurious data will be handling in the following manner:

- There will be no imputations or substitution made for missing safety data points.
- For the PK analyses, imputations will be made for missing data points.

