3.1 General Considerations

All data collected on the electronic case report form (eCRF) will be presented in the data listings and will be listed and sorted by treatment arm, participant number and visit, where applicable. All descriptive summaries will be presented by treatment group and nominal visit/time point (where applicable).

Unless otherwise stated, the following methods will be applied:

- Continuous variables: Descriptive statistics will include the number of non-missing values (n), arithmetic mean, standard deviation (SD), median, minimum and maximum values.

The minimum and maximum values will be displayed to the same decimal precision as the source data, the arithmetic mean, SD and median values will be displayed to one more decimal than the source data for the specific variable.

95% Confidence Intervals (CIs), mean differences (among treatments and from baseline) and least-square (LS-Means) values will be displayed to one more decimal than the source data for a specific variable. P-values will be displayed to 3 decimal places.

The appropriate precision for derived variables will be determined based on the precision of the data on which the derivations are based, and statistics will be presented in accordance with the above-mentioned rules.

- Figures based on continuous summary data:
 - X-axis will represent the linear scheduled time expressed as -Day x for screening values and +Day y on treatment values
 - Y-axis will represent the Mean (+/-SD) and be presented as box-plots (median interquartile) parameter value (unit).
- Categorical variables: Descriptive statistics will include counts and percentages per category. The denominator in all percentage calculations will be the number of participants in the relevant analysis population with non-missing data, unless specifically stated otherwise. Percentages will be displayed to one decimal place. Proportions will be displayed to 3 decimal places.

95% Confidence Intervals (CIs), difference in proportions, odds ratio's and other categorical parameters will be displayed to one decimal place for percentages. Proportions will be displayed to 3 decimal places. P-values will be displayed to 3 decimal places.

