Please note that for this study, first study drug dosing is considered to occur on Day 1.

- **Breakthrough:** Quantifiable HBV DNA increase of $\geq 1 \log_{10}$ HBV DNA copies/mL above LLOQ.
- **Lower limit of quantification (LLOQ):** HBV DNA results i.e HBsAg < LLOQ will be reported as either <LLOQ/Detected (i.e. LLOQ/TD) or <LLOQ/Target Not Detected (i.e. LLOQ/TND), both are considered LLOQ. HBsAg loss rates will be further subdivided accordingly.

- HBsAg decline: Change from Baseline in HBsAg on the log₁₀ scale. Negative values indicate a decline.
- HBsAg loss: Patients with HBsAg < LLOQ/TND.
- HBsAg responder A: A decrease from baseline ≥ 1.0 on the log₁₀ scale, i.e. a change from baseline of ≤ -1.0 . HBsAg results <LLOQ/Target Not Detected will be reported as 0.015 [$\log_{10}(0.015) = -1.852$] and HBsAg < LLOQ/Target Detected will be reported as midpoint between LLOQ/Target Not Detected and LLOQ/Target Detected, i.e. 0.04IU/mL = $\log_{10}(0.04) = -1.4$. Also, HBsAg above LLOQ will be reported as the raw data is reported.
- HBsAg responder B: A decrease from baseline ≥ 0.5 on the log₁₀ scale, i.e. a change from baseline of ≤ -0.5 . HBsAg results <LLOQ/Target Not Detected will be reported as 0.015 [$\log_{10}(0.015) = -1.852$] and HBsAg < LLOQ/Target Detected will be reported as midpoint between LLOQ/Target Not Detected and LLOQ/Target Detected, i.e. 0.04IU/mL = $\log_{10}(0.04) = -1.4$. Also, HBsAg above LLOQ will be reported as the raw data is reported.
- HBsAg Relapse Rate: Patients who became negative (HBsAg<LLOQ), then increased with HBsAg > LLOQ. HBsAg results <LLOQ/Target Not Detected will be reported as 0.015 [$\log_{10}(0.015) = -1.852$] and HBsAg < LLOQ/Target Detected will be reported as midpoint between LLOQ/Target Not Detected and LLOQ/Target Detected, i.e. 0.04IU/mL = $\log_{10}(0.04) = -1.4$. Also, HBsAg above LLOQ will be reported as the raw data is reported.
- Virologic failure: Patients with a confirmed quantifiable HBV DNA increase of $\geq 1 \log_{10}$ HBV DNA copies/mL above LLOQ. HBV DNA results < LLOQ/Target Not Detected will be reported as 10 [$\log_{10}(10) = 1$] and HBV DNA < LLOQ/Target Detected will be reported as midpoint between LLOQ/Target Not Detected and LLOQ/Target Detected, i.e. 20IU/mL = $\log_{10}(20) = 1.3$. Also, HBV DNA above LLOQ will be reported as the raw data is reported.
- HBV-pgRNA decline: Change from Baseline in HBV-pgRNA on the log₁₀ scale. Negative values indicate a decline.

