SD: Standard Deviation. Percentages are calculated (the denominator used for the calculation) based on the number of participants in the ITT Set in each treatment group (N).

*For PCR-based Quantitative HCV Viral Load, percentages are based on the number of anti-HCV positive participants.

Programming note:

- Repeat for table 14.1.3.2 (mITT Set), table 14.1.3.3 (Safety Set) and table 14.1.3.4 (PP Set)

Table 14.1.4 Summary of Treatment Compliance (Safety set)

Category	Group 1 (N=xx)	etc.	Group x (N=xx)
n	xx	xx	xx
< 50% Compliance	xx (xx.x%)	xx (xx.x%)	xx (xx.x%)
>= 50% and =< 80% Compliance	xx (xx.x%)	xx (xx.x%)	xx (xx.x%)
> 80% Compliance	xx (xx.x%)	xx (xx.x%)	xx (xx.x%)

Source Listing: 16.2.5.2, 16.2.5.3

Table 14.2.1.1.x Summary of HBsAg by A Genotype (ITT Set)

Genotype: A

Visit Statistics	Group 1 (N=XXX)		etc.		Group x (N=XXX)	
	Actual Value	Change from Baseline	Actual Value	Change from Baseline	Actual Value	Change from Baseline
Baseline [1]						
N	XX	N/A	XX	N/A	XX	N/A
Mean	XX	N/A	XX	N/A	XX	N/A
SD	XX	N/A	XX	N/A	XX	N/A
Median	XX	N/A	XX	N/A	XX	N/A
Minimum	XX	N/A	XX	N/A	XX	N/A
Maximum	XX	N/A	XX	N/A	XX	N/A
Week 2						
N	XX	XX	XX	XX	XX	XX
Mean	XX	XX	XX	XX	XX	XX
SD	XX	XX	XX	XX	XX	XX
Median	XX	XX	XX	XX	XX	XX
Minimum	XX	XX	XX	XX	XX	XX
Maximum	XX	XX	XX	XX	XX	XX
Week xx						
n	XX	XX	XX	XX	XX	XX
Mean	XX	XX	XX	XX	XX	XX
SD	XX	XX	XX	XX	XX	XX
Median	XX	XX	XX	XX	XX	XX
Minimum	XX	XX	XX	XX	XX	XX
Maximum	XX	XX	XX	XX	XX	XX

Source Listing: 16.2.6.1

SD: Standard Deviation. N/A = Not Applicable.

[1] Baseline is defined as the average of screening and day 1 pre-dose.

Programming Note:

- Repeat for Genotype: Non A

- Repeat for table 14.2.1.1.2 (ITT set with no imputation), 14.2.1.2.1 (mITT with imputation), 14.2.1.2.2 (mITT with no imputation), 14.2.1.3.1 (PP set with imputation) and 14.2.1.3.2 (PP set with no imputation).

Table 14.2.2.x Analysis of HBsAg: Baseline to Week 16 (ITT Set)

	EYP001a 200 mg QD + NA daily (N=XXX)	Placebo + NA daily (N=XXX)
Week 2		
n	XX	XX
Mean change from baseline	XX	XX
LS Mean change from baseline	XX	XX
95% CI on LS mean change from baseline	XX,XX	XX,XX
SE on LS mean change from baseline	xx.xx	xx.xx
p-value	.xxx	.xxx
Difference in change from baseline at Week 10		
N	XX	
Mean	XX	
LS Mean	XX,XX	
95% on LS Mean	XX,XX	
SE on LS Mean	xx.xx	
p-value	.xxx	
<Repeat for Week 4,6,8,10,12,14,16>		

Source Listing: 16.2.6.1

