		n (%) [1]	xx (xx.x %)	xx (xx.x %)
		p-value	0.XXX	

Source Listing: 16.2.6.1

p-value is based on the Person Chi-squared Test.

[1] Number of subjects at each visit (Visit n) will be used as the denominator for the calculation of all percentages.

Programming Note:

- Only to present Week 16 and Week 40 will consider multiplicity by a combination of a hierarchical fixed test procedure and a Hochberg procedure to adjust p-value.

Table 14.2.4.2 Summary and Analysis of HBsAg Responder Rate B (ITT Set)

Visit	Category	Statistics	Decrease from Baseline \geq 0.5 on the log10 Scale	
			EYP001a 200 mg QD + NA daily (N=XXX)	Placebo + NA daily (N=XXX)
Week 16	HBsAg Responder	n	xx	xx
		n (%) [1]	xx (xx.x %)	xx (xx.x %)
		p-value	0.XXX	
Week 40		n	xx	xx
		n (%) [1]	xx (xx.x %)	xx (xx.x %)
		p-value	0.XXX	

Source Listing: 16.2.6.1

p-value is based on the Person Chi-squared Test.

[1] Number of subjects at each visit (Visit n) will be used as the denominator for the calculation of all percentages.

Programming Note:

- Only to present Week 16 and Week 40 will consider multiplicity by a combination of a hierarchical fixed test procedure and a Hochberg procedure to adjust p-value.

Table 14.2.5 Summary of HBsAg Relapse Rate (ITT Set)

Visit	Category	Statistics	Group 1 (N=XXX)	etc.	Group x (N=XXX)
Week 16		n	xx	xx	xx
	HBsAg Relapse	n (%) [1]	xx (xx.x %)	xx (xx.x %)	xx (xx.x %)
<Repeat for Week 20, 28, 40>		n	xx	xx	xx
	HBsAg Relapse	n (%) [1]	xx (xx.x %)	xx (xx.x %)	xx (xx.x %)

Source Listing: 16.2.6.1

HBsAg Relapse is defined as patients who became negative [HBsAg < LLOQ], then increased with HBsAg > LLOQ.
 [1] Number of subjects at each visit (Visit n) will be used as the denominator for the calculation of all percentages.

Table 14.2.6 Summary of Virologic Failure Rate of HBV DNA (ITT Set)

Visit	Category	Statistics	Group 1 (N=XXX)	etc.	Group x (N=XXX)
Week 16		n	xx	xx	xx
	Virologic Failure Rate	n (%) [1]	xx (xx.x %)	xx (xx.x %)	xx (xx.x %)
<Repeat for Week 20, 28, 40>		n	xx	xx	xx
	Virologic Failure Rate	n (%) [1]	xx (xx.x %)	xx (xx.x %)	xx (xx.x %)

Source Listing: 16.2.6.2

Virologic Failure Rate of HBV DNA is defined as patients with a confirmed quantifiable HBV DNA increase of $\geq 1\log_{10}$ HBV DNA copies/mL above LLOQ.
 [1] Number of subjects at each visit (Visit n) will be used as the denominator for the calculation of all percentages.

Table 14.2.7 Summary of HBV-pgRNA (ITT Set)

Visit	Group 1 (N=XXX)		etc.		Group x (N=XXX)	

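### Mock Table 14.2.5 divides HBsAg relapses by all patients at the visit, although only those with earlier HBsAg loss can relapse

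*SAP*

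**What the plan says.** Protocol 2.2.2 and SAP 2.3.2 list the HBsAg relapse rate as a secondary efficacy endpoint at Weeks 16, 20, 28 and 40. SAP 3.2 has the entry "HBsAg Relapse Rate: Patients who became negative (HBsAg<LLOQ), then increased with HBsAg > LLOQ", which says who has relapsed but gives no denominator. Mock Table 14.2.5 (ITT set) repeats the definition, "HBsAg Relapse is defined as patients who became negative [HBsAg < LLOQ], then increased with HBsAg > LLOQ", and supplies a denominator in its footnote: "Number of subjects at each visit (Visit n) will be used as the denominator for the calculation of all percentages".

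The general rules point the same way. SAP 3.1: "The denominator in all percentage calculations will be the number of participants in the relevant analysis population with non-missing data, unless specifically stated otherwise". Protocol 11.1, unless stated otherwise: "the number of patients in the treatment group (for the specific analysis set) will be used as the denominator for all percentage calculations". Nothing in either document limits the relapse denominator to patients who had lost HBsAg.

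Inclusion criterion 4a (Protocol 4.2) is "HBV DNA <LLOQ and serum HBsAg >100 IU/mL", so every patient enters HBsAg-positive.

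Elsewhere the SAP shells do restrict to eligible patients. For HCV viral load (mock Table 14.1.3.x), "percentages are based on the number of anti-HCV positive participants". Childbearing potential is a percentage of females (mock Table 14.1.2.x), and Table 14.2.9 covers HBeAg-positive patients only.

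Protocol 11.3.3.2 summarises relapse by counts and percentages, without a test.

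**The concern.** Relapse presupposes a loss. With all patients at the visit in the denominator, the percentage mixes how often HBsAg is lost with how often it returns. A low figure can mean that losses lasted or that there were hardly any. The extreme case is an arm in which nobody clears HBsAg: the table prints 0 relapses over a full visit n, which reads as an absence of relapse when no patient could have had one. At stake is the meaning of a named secondary endpoint in a trial whose title refers to functional cure.

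**Working it through.** **Inputs.** Arms of 37 and 12 (SAP 2.5). Assumed HBsAg loss 10% on EYP001a and 0.5% on placebo (SAP 2.4 and 3.4). The documents give no relapse risk among patients who lose HBsAg, so that risk, r, is an assumption. It is set equal in both arms and varied.

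**1. The plan's own figure on these loss rates.** It states power of about 55% for the loss rate (one-sided 0.05, un-pooled variance).

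SE = √(0.005 × 0.995/12 + 0.10 × 0.90/37) = 0.0534; power = Φ(0.095/0.0534 − 1.645) = 55.4%. The figure is reproduced, so the inputs are read as the plan intends.

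**2. Expected number at risk of relapse.** 37 × 0.10 = 3.7 on EYP001a; 12 × 0.005 = 0.06 on placebo.

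**3. What the table prints on average.** Printed percentage = loss rate × r.

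| r (assumed, both arms) | EYP001a as tabulated | Placebo as tabulated | Among patients with prior loss |
|---|---|---|---|
| 10% | 1.0% | 0.05% | 10% |
| 25% | 2.5% | 0.13% | 25% |
| 50% | 5.0% | 0.25% | 50% |
| 75% | 7.5% | 0.38% | 75% |
| 100% | 10.0% | 0.50% | 100% |

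The whole range of r is squeezed into 0 to 10% on EYP001a and 0 to 0.5% on placebo. With identical r, the expected figures differ by 10%/0.5% = 20-fold because of the loss rates alone.

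**4. Worked example.** If 4 of 37 lose HBsAg and 2 relapse, the table prints 2/37 = 5.4%. Among those at risk it is 2/4.

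**5. An arm with no losses.** P(no placebo patient loses HBsAg) = 0.995^12 = 94.2%. SAP section 15 says enrolment was suspended after about 25 randomisations. Assuming a 19:6 split, 1.9 and 0.03 losses are expected, and 0.995^6 = 97.0%.

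**6. Can the number at risk be read from another table?** Loss Tables 14.2.3.1 and 14.2.3.2 show Weeks 16 and 40; Table 14.2.11 shows Weeks 16, 20, 28 and 40. HBsAg is sampled at every treatment visit (Protocol 7.1). A patient who clears at Week 8 and is positive again by Week 16 meets the relapse definition but appears as a loss in none of these tables. They also give per-visit counts, not the number who had ever lost HBsAg. Only Listing 16.2.6.1 allows it to be rebuilt.

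**The case against.** - **The table may show what was intended.** The endpoint wording can be read as the share of all patients who lose and then regain HBsAg. No secondary objective mentions relapse or durability, and the footnote follows the general denominator rules. This stands as far as it goes: the all-patient figure is a legitimate quantity, but its label does not say which quantity it is, and it does not describe relapse.
- **Nothing rests on it.** The endpoint has no p-value, is outside the Hochberg family (SAP 3.4) and the inferential list (SAP 12.1), and is not marked for either DSMC meeting (SAP section 18). This stands.
- **The 10% loss rate may be generous.** The imputed value of 0.04 IU/mL is described as a midpoint above 0.015, which suggests an LLOQ near 2 × 0.04 − 0.015 = 0.065; the documents do not state it. From the entry minimum of 100 IU/mL, reaching 0.065 to 0.04 needs a fall of about 3.2 to 3.4 log10. With the planned mean of −1.0 (assuming no placebo change), SD 1.08 and normality, that is about 2.1% to 1.3% of patients, or 0.8 to 0.5 of 37, and fewer from higher baselines. An empty table is then likely. That weakens the 5% illustration, but in an empty table a zero over a full visit n needs the at-risk count most.
- **The at-risk subset is formed after randomisation** and is usually empty on placebo. This stands: the corrected figure cannot serve as a comparison of arms.

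A reader might go further and infer that the comparison is reversed, so that EYP001a looks worse because it works while placebo scores a perfect 0%. The documents do not support that. No between-arm comparison of relapse is planned. EYP001a shows a higher figure only if at least one of its patients relapses; on the plan's loss rate that has probability 1 − (1 − 0.10r)^37, which is 31% at r = 10%, 85% at r = 50% and 98% at r = 100%. Under the general comments to the mock tables a zero count prints without a percentage. Counts already stand beside the percentages, and losses are tabulated elsewhere.

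**Conclusion.** The point holds as a defect of description, and it is minor. The denominator includes patients who cannot have the event, no other rule repairs it, and the SAP restricts denominators to eligible patients elsewhere. On the plan's loss rates and an assumed common relapse risk of 50%, the table would average about 5% and 0.25% where the risk among patients with prior loss is 50%. The size depends on r, which the documents do not give, and on a 10% loss rate that may be optimistic. That the percentage is a product of two quantities, and that an arm without losses shows 0 with nobody at risk, depends on neither. No error rate, power or stopping decision is affected.

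**What to change.** In SAP 3.2 and Table 14.2.5:

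- Add a row for the number of patients with HBsAg below LLOQ at any earlier visit and a value at this visit.
- Report relapsers as n/N of that row, and print 'not applicable' when N = 0. In the same line, say whether a relapse is counted only at the visit or carried forward.
- Label the result as descriptive within a post-randomisation subset, not a randomised comparison.
- If the all-patient percentage is kept, label it 'loss then relapse, all patients'.

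The cost is one derivation line, one table row and one footnote, from HBsAg values already collected. The general comments to the mock tables already allow footnotes to be amended.
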